7.15 Pharmacogenetics

7.15.1 Blood Sample Collection and Processing

Peripheral blood will be collected from enrolled patients at C1 D1 into (1) 10 mL EDTA lavender top tube. Genomic DNA will be extracted from the blood samples, using the QIAamp DNA isolation kit from Qiagen (Valencia, CA) and following the manufacturer's instructions.

7.15.2 Sample Handling and Shipment

Whole blood samples collected at RPCI will be sent on ice for processing the same day of collection.

Whole blood samples collected at participating sites will be frozen and stored at -70° until batched shipped monthly Monday - Thursday. Do not ship specimens on Fridays or on day before a holiday. Packaging should be clearly labelled as follows with e-mail notification:

Roswell Park Cancer Institute
Grace Cancer Drug Center (GCDC) Room 151
Attn: [name] – I 225612
[name]
[name]
[contact]
[contact]

8 EFFICACY EVALUATIONS

8.1 Objective Tumor Response

All protocol-defined imaging studies must be performed at the investigative site or sponsor-approved facility using protocol-defined parameters. The same method of assessment and the same technique should be used to characterize each identified and reported lesion at baseline and during follow-up. RECIST 1.1 will be used to assess objective tumor response.

8.2 Target Lesions

All measurable lesions up to a maximum of 2 lesions per organ and 5 lesions in total, representative of all involved organs, will be identified as target lesions and recorded and measured at baseline. Target lesions will be selected on the basis of their size. Lesions with the longest diameter (short axis for lymph nodes) and are ≥ 10 mm (CT and MRI), ≥ 15 mm lymph nodes, > 20 mm CXR and are for accurate repetitive measurements (either by imaging techniques or clinically) will be chosen. A sum of the longest diameter (short axis for lymph nodes) of all target lesions will be calculated and reported as the baseline sum diameters. This will be used as reference to further characterize the objective tumor response of the measurable dimension of the disease.

- **Complete Response (CR):** Disappearance of all target lesions. Any lymph nodes must have a reduction in short axis to < 10 mm. Changes in tumor measurements must be confirmed by repeat studies performed no less than 6 weeks after the criteria for response are first met.
- **Partial Response (PR):** At least a 30% decrease in the sum of diameters of target lesions, taking as reference the baseline sum diameters. Changes in tumor measurements must be confirmed by repeat studies performed no less than 6 weeks after the criteria for response are first met.
- **Progressive Disease (PD):** At least a 20% increase in the sum of diameters of target lesions, taking as references the smallest sum on study (this includes the baseline sum if that is the smallest on study). In addition to the relative increase of 20%, the sum must also demonstrate an absolute increase of at least 5 mm. The appearance of one or more new lesions is also considered progression.
- **Stable Disease (SD):** Neither sufficient shrinkage to qualify for PR nor sufficient increase to qualify for PD, taking as reference the smallest sum diameter while on study. Subjects having a documented response with no confirmation of the response will be listed with stable disease.

8.3 Non-Target Lesions

All other small lesions (longest diameter < 10 mm or lymph nodes ≥ 10 mm to < 15 mm short axis) and non-measurable lesions (i.e., leptomeningeal disease, ascites, pleural or pericardial effusion, inflammatory breast disease, lymphangitic involvement of skin or lung, blastic bone lesions, or abdominal masses/abdominal organomegaly identified by physical exam that is not measurable by imaging) should be identified as non-target lesions and indicated as present in the source documents at baseline. The general location will also be documented on the images drawing a regularly-shaped Region of Interest. Measurements of the non-target lesions will not be performed, but the presence or absence of each should be noted throughout follow-up and evaluation.

- **Complete Response:** Disappearance of all non-target lesions and normalization of tumor marker level, if applicable. All lymph nodes must be non-pathological in size (< 10 mm short axis).
- **Non-Complete Response/Non-Progressive Disease:** Persistence of 1 or more non-target lesion(s) and/or maintenance of tumor marker level above the upper limits of normal.
- **Progressive Disease:** Appearance of 1 or more new lesions or the unequivocal progression of existing non-target lesions. Although a clear progression of non-target lesions is exceptional, in such circumstances, the opinion of the treating physician should prevail and the progression status should be confirmed at a later time.

8.4 Evaluation of Response

Time point response assessments will be performed every other cycle (timed to coincide with the end of a cycle) with a confirmatory assessment (required for non-randomized trials) no less than

4 weeks after a PR or CR is deemed. To determine time point response, refer to **Table 5** and **Table 6**.

Table 5. Time Point Response Criteria (+/- non-target disease)

Target Lesions	Non-Target Lesions	New Lesions	Overall Response
CR	CR	No	CR
CR	Non-CR/Non-PD	No	PR
CR	Not evaluated	No	PR
PR	Non-PD or not all evaluated	No	PR
SD	Non-PD or not all evaluated	No	SD
Not all evaluated	Non-PD	No	NE
PD	Any	Yes or No	PD
Any	PD	Yes or No	PD
Any	Any	Yes	PD

Table 6. Time Point Response Criteria (non-target disease only)

Non-Target Lesions	New Lesions	Overall Response
CR	No	CR
Non-CR/non-PD	No	Non-CR/non-PD ¹
Not all evaluated	No	NE
Unequivocal PD	Yes or No	PD
Any	Yes	PD

¹ Non-CR/non-PD is preferred over SD for non-target disease since SD is used as endpoint for assessment of efficacy in trials so to assign this category when no lesions can be measured is not advised.

The best overall response is the best response recorded from the start of study treatment until progression or death or discontinuation for any reason (the end of treatment taking into account any requirement for confirmation). In general, the subject's best response assignment will depend on the achievement of both measurement and confirmation criteria and will be determined by combining the subject's status of target lesions, non-target lesions, and new lesions.

- **Symptomatic Deterioration:** Subjects with global deterioration of health status requiring discontinuation of treatment without objective evidence of disease progression at that time, and not related to study treatment or other medical conditions should be reported as progressive disease due to "symptomatic deterioration." Every effort should be made to document objective progression even after discontinuation of treatment due to symptomatic deterioration. Symptomatic deterioration that may lead to discontinuation of treatment include, but is not limited to, symptoms such as:

- Weight loss > 10% of body weight.

- Worsening of disease-related symptoms (e.g., worsening dyspnea, increasing pain/increasing requirement for narcotic analgesics).
- Decline in performance status of > 1 level on ECOG scale.

8.5 Confirmation Measurement

The main goal of confirmation of objective response in clinical trials is to avoid overestimating the response rate observed. This aspect of response evaluation is particularly important in nonrandomized trials where response is the primary endpoint. In this setting, to be assigned a status of partial response or complete response, changes in tumor measurements must be confirmed by repeat assessments that should be performed no less than 4 weeks after the criteria for response are first met. Longer intervals as determined by the study protocol may also be appropriate.

In the case of stable disease, measurements must have met the stable disease criteria at least once after study entry at a minimum interval (in general, not less than 6 – 8 weeks).

8.6 Guidelines for Evaluation of Measurable Disease

All measurements should be taken and recorded in metric notation using a ruler or calipers. All baseline evaluations should be performed as closely as possible to the beginning of treatment and never more than 4 weeks before the beginning of the treatment.

The same method of assessment and the same technique should be used to characterize each identified and reported lesion at baseline and during follow-up. Imaging-based evaluation is preferred to evaluation by clinical examination unless the lesion(s) being followed cannot be imaged but are assessable by clinical exam.

- **Clinical Lesions:** Clinical lesions will only be considered measurable when they are superficial (e.g., skin nodules and palpable lymph nodes) and ≥ 10 mm diameter as assessed using calipers (e.g., skin nodules). In the case of skin lesions, documentation by color photography, including a ruler to estimate the size of the lesion, is recommended.
- **Chest x-ray:** Lesions on chest x-ray are acceptable as measurable lesions when they are clearly defined and surrounded by aerated lung. However, CT is preferable.
- **Conventional CT and MRI:** This guideline has defined measurability of lesions on CT scan based on the assumption that CT slice thickness is 5 mm or less. If CT scans have slice thickness greater than 5 mm, the minimum size for a measurable lesion should be twice the slice thickness. MRI is also acceptable in certain situations (e.g., for body scans).

Use of MRI remains a complex issue. MRI has excellent contrast, spatial, and temporal resolution; however, there are many image acquisition variables involved in MRI, which greatly impact image quality, lesion conspicuity, and measurement. Furthermore, the availability of MRI is variable globally. As with CT, if an MRI is performed, the technical specifications of the scanning sequences used should be optimized for the evaluation of the type and site of disease. Furthermore, as with CT, the modality used at follow-up should be the same as was used at baseline and the lesions should be measured/assessed on the same pulse sequence. It is beyond

the scope of the RECIST guidelines to prescribe specific MRI pulse sequence parameters for all scanners, body parts, and diseases. Ideally, the same type of scanner should be used and the image acquisition protocol should be followed as closely as possible to prior scans. Body scans should be performed with breath-hold scanning techniques, if possible.

- **PET-CT:** At present, the low dose or attenuation correction CT portion of a combined PET-CT is not always of optimal diagnostic CT quality for use with RECIST measurements. However, if the site can document that the CT performed as part of a PET-CT is of identical diagnostic quality to a diagnostic CT (with IV and oral contrast), then the CT portion of the PET-CT can be used for RECIST measurements and can be used interchangeably with conventional CT in accurately measuring cancer lesions over time. Note, however, that the PET portion of the CT introduces additional data which may bias an investigator if it is not routinely or serially performed.
- **Ultrasound:** Ultrasound is not useful in assessment of lesion size and should not be used as a method of measurement. Ultrasound examinations cannot be reproduced in their entirety for independent review at a later date and, because they are operator dependent, it cannot be guaranteed that the same technique and measurements will be taken from one assessment to the next. If new lesions are identified by ultrasound in the course of the study, confirmation by CT or MRI is advised. If there is concern about radiation exposure at CT, MRI may be used instead of CT in selected instances.
- **Endoscopy, Laparoscopy:** The utilization of these techniques for objective tumor evaluation is not advised. However, such techniques may be useful to confirm complete pathological response when biopsies are obtained or to determine relapse in trials where recurrence following complete response (CR) or surgical resection is an endpoint.
- **Tumor Markers:** Tumor markers alone cannot be used to assess response. If markers are initially above the upper normal limit, they must normalize for a subject to be considered in complete clinical response.
- **Cytology, Histology:** These techniques can be used to differentiate between partial responses (PR) and complete responses (CR) in rare cases (e.g., residual lesions in tumor types, such as germ cell tumors, where known residual benign tumors can remain).

The cytological confirmation of the neoplastic origin of any effusion that appears or worsens during treatment when the measurable tumor has met criteria for response or stable disease is mandatory to differentiate between response or stable disease (an effusion may be a side effect of the treatment) and progressive disease.

- **FDG-PET:** While FDG-PET response assessments need additional study, it is sometimes reasonable to incorporate the use of FDG-PET scanning to complement CT scanning in assessment of progression (particularly possible 'new' disease). New lesions on the basis of FDG PET imaging can be identified according to the following algorithm:
- Negative FDG-PET at baseline, with a positive FDG-PET at follow-up is a sign of PD based on a new lesion.

- No FDG-PET at baseline and a positive FDG-PET at follow-up: If the positive FDG-PET at follow-up corresponds to a new site of disease confirmed by CT, this is PD. If the positive FDG-PET at follow-up is not confirmed as a new site of disease on CT, additional follow-up CT scans are needed to determine if there is truly progression occurring at that site (if so, the date of PD will be the date of the initial abnormal FDG-PET scan). If the positive FDG-PET at follow-up corresponds to a pre-existing site of disease on CT that is not progressing on the basis of the anatomic images, this is not PD.
- FDG-PET may be used to upgrade a response to a CR in a manner similar to a biopsy in cases where a residual radiographic abnormality is thought to represent fibrosis or scarring. The use of FDG-PET in this circumstance should be prospectively described in the protocol and supported by disease-specific medical literature for the indication. However, it must be acknowledged that both approaches may lead to false positive CR due to limitations of FDG-PET and biopsy resolution/sensitivity.

Note: A ‘positive’ FDG-PET scan lesion means one which is FDG avid with an uptake greater than twice that of the surrounding tissue on the attenuation corrected image.

9 SAFETY EVALUATION

9.1 Adverse Events

9.1.1 Definition

An adverse event or adverse experience (AE) is any untoward medical occurrence associated with the use of a drug in humans, whether or not considered drug related. Therefore, an AE can be ANY unfavorable and unintended sign (including an abnormal laboratory finding), symptom, or disease temporally associated with the use of a medicinal (investigational) product, whether or not considered related to the medicinal (investigational) product (attribution of ‘unrelated’, ‘unlikely’, ‘possible’, ‘probable’, or ‘definite’).

An AE is considered “unexpected” if it is not listed in the investigator brochure or is not listed at the specificity or severity that has been observed; or if an investigator brochure is not required or available, is not consistent with the risk information described in the general investigational plan in other study-related documents.

9.1.1.1 Diagnosis Versus Signs and Symptoms

If known, a diagnosis should be recorded on the CRF rather than individual signs and symptoms (e.g., record only liver failure or hepatitis rather than jaundice, asterix, and elevated transaminases). However, if a constellation of signs and/or symptoms cannot be clinically characterized as a single diagnosis or syndrome at the time of reporting, each individual event should be recorded as an AE or SAE on the CRF. If a diagnosis is subsequently established, it should be reported as follow-up information.

9.1.1.2 Adverse Events Occurring Secondary to Other Events

In general, AEs occurring secondary to other events (e.g., cascade events or clinical sequelae) should be identified by their primary cause. For example, if severe diarrhea is known to have resulted in dehydration, it is sufficient to record only diarrhea as an AE or SAE on the CRF.

However, clinically significant AEs occurring secondary to an initiating event that are separated in time should be recorded as independent events on the CRF. For example, if a severe gastrointestinal hemorrhage leads to renal failure, both events should be recorded separately on the CRF.

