1.3.2 Clinical Safety

As of July 2012, a total of 397 patients across all clinical studies (completed and ongoing; single-agent and combination therapy) have received at least 1 administration of NKTR-102. Safety data from 309 patients are included in the Investigator's Brochure, version 8.0. Observations across all studies (including safety data from ongoing studies) have been generally consistent with regard to the overall safety profile of NKTR-102. Gastrointestinal toxicity, especially diarrhea, is the most common and clinically significant toxicity occurring with the use of NKTR-102. Other frequently observed AEs have been nausea, vomiting, fatigue, and dehydration (secondary to diarrhea and/or vomiting). Diarrhea and dehydration were also the most common serious adverse events (SAEs) across all studies evaluating NKTR-102. The incidence of Grade 3 diarrhea in the Phase II study in patients with metastatic breast cancer (MBC) at the recommended dose and schedule equaled 23%, with 11% Grade 3 dehydration and 6% Grade 3 vomiting (there was no Grade 4 diarrhea, dehydration or vomiting). Prolonged severe diarrhea with associated dehydration leading to pre-renal azotemia/kidney failure has been fatal in 3 patients in the ongoing Phase II studies in metastatic colorectal, ovarian, and breast cancers (one each of an ovarian cancer and breast cancer patient on the 14-day schedule; one CRC patient on the 21-day schedule). Early cholinergic toxicities (including diarrhea), commonly associated with irinotecan, has not been observed with the use of NKTR-102 in any of the completed or ongoing clinical studies. Late-onset, severe diarrhea can occur: the median

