3.2 Secondary Objectives

- To evaluate the objective response rate.
- To evaluate the duration of response.
- To evaluate the overall survival.
- To evaluate the toxicity of NKTR-102 in this patient population.

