Grade 1 or Grade 2	Consider anti-emetic and/or anti-diarrheal therapy. If Grade 2 present on a treatment day, hold therapy for a week or until toxicity resolves to baseline or Grade \leq 1, with a maximum of 28 days.	Consider prophylactic anti-emetic therapy. Maintain dose level.
Grade 3	Use anti-emetic and/or anti-diarrheal therapy. If present on a treatment day, hold therapy for a week or until toxicity resolves to baseline or Grade \leq 1, with a maximum of 28 days.	Consider prophylactic anti-emetic therapy. \downarrow 1 dose level after 1st occurrence; \downarrow 1 dose level after 2nd occurrence Discontinue patient after 3rd occurrence
Grade 4	Use anti-emetic therapy and IV fluids. Consider hospital admission. If present on a treatment day, hold therapy for a week or until toxicity resolves to baseline or Grade \leq 1, with a maximum of 28 days.	Use prophylactic anti-emetic therapy. \downarrow 2 dose level after 1st occurrence. Discontinue patient after 2nd occurrence.
Nausea / Vomiting / Abdominal Pain		
Grade 1 or Grade 2	Consider anti-emetic therapy. If Grade 2 present on a treatment day, hold therapy for a week or until toxicity resolves to baseline or Grade \leq 1, with a maximum of 28 days.	Consider prophylactic anti-emetic therapy. Maintain dose level.
Grade 3 or Grade 4	Use anti-emetic therapy. Consider administration of IV fluids. If present on a treatment day, hold therapy for a week or until toxicity resolves to baseline or Grade \leq 1, with a maximum of 28 days.	After 1st occurrence use prophylactic anti-emetic therapy and maintain dose level \downarrow 1 dose level after 2nd occurrence Discontinue patient after 3rd occurrence
Other Drug-Related Non-Hematologic Toxicities (Except Fatigue/Asthenia and Alopecia)		
Grade 1 or Grade 2	Consider supportive care as appropriate. If Grade 2 present on a treatment day, hold therapy for a week or until toxicity resolves to baseline or Grade \leq 1, with a maximum of 28 days.	Maintain dose level (for Grade 2 toxicity, the Investigator may use discretion to \downarrow 1 dose level after 1 st occurrence depending on the nature of the toxicity).
Grade 3 or Grade 4	Use supportive care as appropriate. If present on a treatment day, hold therapy for a week or until toxicity resolves to baseline or Grade \leq 1, with a maximum of 28 days.	\downarrow 1 dose level after 1 st occurrence; supportive care as appropriate. \downarrow 1 dose level after 2 nd occurrence. Discontinue patient after 3 rd occurrence.

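### The recording rule in Section 9.1.1.2 lets dehydration caused by severe diarrhea go unrecorded, so the adverse event tables can under-count a known serious toxicity, and unevenly between sites

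*Combined protocol and SAP*

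**What the plan says.** Section 9.1.1.2 tells sites, as a general rule, to identify a secondary event by its primary cause. Its worked example is that "if severe diarrhea is known to have resulted in dehydration, it is sufficient to record only diarrhea", whether as an AE or an SAE. There is one exception: "clinically significant AEs occurring secondary to an initiating event that are separated in time should be recorded as independent events". The example given for the exception is gastrointestinal hemorrhage leading to renal failure.

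Other sections treat dehydration as an event in its own right:

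- Section 1.3.2 (Clinical Safety) describes it as secondary to diarrhea, vomiting or both, and states that "Diarrhea and dehydration were also the most common serious adverse events (SAEs) across all studies evaluating NKTR-102". For the breast cancer Phase II study it reports 23% Grade 3 diarrhea, "with 11% Grade 3 dehydration and 6% Grade 3 vomiting". It also places dehydration in the sequence that was fatal in 3 patients.
- Table 3 (Section 7.2.3) has separate dehydration rows for Grade 1 or 2, Grade 3 and Grade 4, with consequences that depend on grade and occurrence.
- Section 3.2 lists the secondary objective "To evaluate the toxicity of NKTR-102 in this patient population".
- The synopsis (Safety Assessments) plans frequency tables of each patient's maximum grade for each type of AE. Section 11.1 plans a summary of all AEs overall and by group. Section 11.6 plans tables of the number and severity of all AEs, with Grade 3 and higher summarized as well.

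**The concern.** The example in the recording rule is the very chain of events that the background section identifies as important for this drug. A site that enters diarrhea alone has complied with the protocol, and so has a site that enters both events. The dehydration count then depends partly on site habit.

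Three things are at stake. The first is the dehydration line in the AE and SAE tables, which serves a secondary objective. The second is consistency between sites in a multi-site trial of 38 patients, where a few cases decide what the line shows. The third is traceability: Table 3 acts on dehydration by grade and by occurrence, and neither could be checked from the AE data for an episode that was not entered.

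**Working it through.** The plan states no figure for this point, so there is none to reproduce. The check is a comparison of sections followed by an illustration of size.

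**Comparison of sections**

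1. *Does the rule allow omission?* Yes. Section 9.1.1.2 calls a diarrhea entry alone sufficient, for an AE or an SAE.
2. *Does it require omission?* No. It opens with a general qualifier, and sufficiency does not forbid a second entry.
3. *Does the exception restore the record?* Only for clinically significant sequelae that are separated in time. The section itself puts diarrhea leading to dehydration on the side that need not be recorded.
4. *Do the planned tables recover dehydration from elsewhere?* No. The synopsis, Section 11.1 and Section 11.6 summarize AEs as recorded, and no section derives dehydration from another source.
5. *Which way can the error go?* The rule permits entries to be left out and never adds one, so it can only lower the dehydration count.

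**Illustration of size**

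Inputs:

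- n = 38, the planned maximum (Section 4.2).
- p = 0.11, the Grade 3 dehydration rate in the breast cancer Phase II study (Section 1.3.2). Carrying it over to relapsed SCLC is an assumption.
- s, the share of patients with Grade 3 dehydration whose event is folded into diarrhea. The documents do not give it, so the full range is shown.

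Formulas:

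- Expected number recorded = 38 × 0.11 × (1 − s) = 4.18 × (1 − s)
- Probability that the table shows no Grade 3 case = (1 − 0.11 × (1 − s))^38

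| Share folded, s | Recorded rate | Expected number recorded | Probability of no recorded case |
|---|---|---|---|
| 0% | 11.0% | 4.2 | 1.2% |
| 25% | 8.25% | 3.1 | 3.8% |
| 50% | 5.5% | 2.1 | 11.7% |
| 75% | 2.75% | 1.0 | 34.7% |
| 100% | 0% | 0 | 100% |

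For s = 50%: 4.18 × 0.5 = 2.09, and (1 − 0.055)^38 = 0.117.

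The bottom row needs every case to be caused by severe diarrhea and every site to skip the optional entry. Section 1.3.2 also names vomiting as a cause, and the worked example does not mention vomiting. The row is a bound, not a forecast.

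**The case against.** The strongest reply is that little is lost. The wording is permissive. The initiating severe diarrhea is still recorded and still appears in the Grade 3 and higher tables. Section 7.2 requires dose reductions and delays to be entered in the eCRF. Section 9.2.2 requires an SAE form with a narrative, so a serious case of dehydration can usually be found there. Table 3 acts on the toxicity observed, not on the AE page. Its Grade 3/4 diarrhea row already calls for two levels after a first occurrence, against one level for Grade 3 dehydration and two for Grade 4, so a first dose step would normally have a matching diarrhea entry. The safety analysis is descriptive, and no hypothesis test or stated stopping rule uses the dehydration count.

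All of that stands, and it limits the harm to safety data and traceability. It does not put the dehydration grade and count back into the tables, which are organized by event type.

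A reader might also be tempted by stronger inferences that the documents do not support:

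- *That dehydration will be under-counted, or reported as 0%.* Sites may record it, and the share folded is unknown.
- *That the exception for events separated in time is empty because dehydration normally accompanies the diarrhea.* No section gives the timing of one relative to the other.
- *That the result could not be compared with earlier NKTR-102 trials.* The recording conventions of those trials are not described.
- *That renal failure and neutropenic sepsis are lost in the same way.* Section 9.1.1.2 uses renal failure after a gastrointestinal event as its example of separate recording. Sections 1.3.2 and 1.5 present neutropenia as myelosuppression that may occur in the setting of diarrhea or dehydration, which does not place sepsis clearly under the rule.

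**Conclusion.** The point holds as a data-recording weakness. Section 9.1.1.2 permits dehydration to be left out in the situation most relevant to this drug, so the planned AE and SAE tables can under-count it, and can do so inconsistently between sites. That the rule can only push the count down follows from the text and needs no assumption.

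The size is not determined by the documents. The range of 4.2 down to 0 recorded Grade 3 cases rests on the breast cancer rate applying here, on that rate being a complete count, and on an unknown folding share. The primary endpoint is unaffected. Because a partial trace remains in the diarrhea entries, dose-change records and SAE narratives, this is an inexpensive improvement that should be made, not a defect that threatens the trial's main conclusion.

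**What to change.** In Section 9.1.1.2, replace the worked example with one that does not involve dehydration. Add a sentence to this effect: in this trial, dehydration is always recorded as its own AE (or SAE, where it meets the definition), with its own CTCAE grade, and linked to the event that caused it.

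The cost is one edited paragraph and a few extra AE lines, for about four patients at Grade 3 under the illustrative rate plus any at other grades. The small downside is that one clinical episode can appear on two lines of the tables; the link lets the analyst identify such pairs and footnote them. No dose or clinical management rule changes.
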